## LIST OF ABBREVIATIONS AND DEFINITION OF TERMS

Abbreviation	Definition
AE	Adverse event
ATC	Anatomic therapeutic class
BBS	Bardet-Biedl syndrome
█	█
CI	Confidence interval
cm	Centimeter
CRF	Case report form
CSR	Clinical study report
C-SSRS	Columbia-Suicide Severity Rating Scale
CTCAE	Common Terminology Criteria for Adverse Events
ECG	Electrocardiogram
FAS	Full Analysis Set
FDA	Food and Drug Administration
█	█
HR	Heart rate
ICH	International Conference on Harmonisation
IEC	Independent Ethics Committee
IRB	Institutional Review Board
IRT	interactive response technology
ISR	Injection site reaction
kg	Kilogram
LEPR	Leptin receptor
LTE	Long-term extension
m 	Meters squared
MC4R	Melanocortin-4 receptor
MedDRA	Medical Dictionary for Regulatory Activities
mg	Milligram
MSH	Melanocyte-stimulating hormone
N	Number
NCI	National Cancer Institute
nM	Nanometer
%	Percent
PCSK1	Proprotein convertase subtilisin/kexin type 1
PK	Pharmacokinetic
POMC	Pro-opiomelanocortin

Abbreviation	Definition
PPL	POMC (pro-opiomelanocortin), PCSK1 (proprotein convertase subtilisin/kexin type 1), LEPR (leptin receptor)
PPS	Per Protocol Set
PR	PR interval
PT	Preferred term
QD	Once daily Setmelanotide
QRS	Interval between Q, R, and S waves
QT	Interval between Q and T waves
QW	Once weekly Setmelanotide
Rel Day	Relative study day
RGDO	Rare genetic disorder of obesity
RM-493	Setmelanotide
SA	Safety analysis set
SAE	Serious adverse event
SAP	Statistical analysis plan
SC	Subcutaneous
SD	Standard deviation
SI	International System of Units
SoA	Schedule of Assessments
SOC	System organ class
TEAE	Treatment-emergent adverse event
US	United States
VC	Vital capacity
WHO	World Health Organization

## 1. INFORMATION FROM THE STUDY PROTOCOL

### 1.1. Introduction and Objectives

#### 1.1.1. Introduction

This statistical analysis plan (SAP) summarizes the planned [REDACTED], safety and pharmacokinetic (PK) analyses for study RTHM-493-037, which is a Phase 3, double-blind, randomized, crossover to open label, multicenter trial to examine the effects of a combinatory once daily (QD) and once weekly (QW) formulation of setmelanotide. A sterile solution of [REDACTED] will be used for daily administration and a [REDACTED] will be used for weekly administration. The [REDACTED] technology transforms the injected drug into a gel which releases drug slowly by diffusion from the subcutaneous (SC) depot. The purpose of this study is to compare the QD and QW formulations of setmelanotide in patients with the following rare genetic disorders of obesity (RGDO): biallelic PPL (POMC [pro-opiomelanocortin], PCSK1 [proprotein convertase subtilisin/kexin Type 1], LEPR [leptin receptor]), heterozygous PPL, and patients with BBS (Bardet-Biedl syndrome).

Obesity is a multifactorial disease caused by various environmental, neurobehavioral, immunological, endocrine, medical, and genetic/epigenetic factors or a complex interplay between 2 or more of these factors ([Maes 1997](#); [Schousboe 2003](#); [Silventoinen 2010](#); [Hall 2012](#); [Pigevre 2016](#); [Sheikh 2017](#); [Thaker 2017](#)). In a subset of individuals with obesity, rare genetic variants may result in severe obesity. The identification of key genetic determinants of the neuronal pathways and signaling molecules (e.g., leptin) regulating appetite and body weight has led to the discovery of multiple RGDO ([van der Klaauw 2015](#)). A key neuronal pathway, the central melanocortin and melanocortin-4 receptor (MC4R) pathway, plays an important role in appetite, hunger, and energy utilization. The melanocortins are a family of peptide hormones (including adrenocorticotrophic hormone,  $\alpha$ -melanocyte-stimulating hormone [MSH],  $\beta$ -MSH, and  $\gamma$ -MSH) derived from the common precursor, POMC. Originating in the hypothalamus, the MC4R pathway concertedly modulates appetite (feelings of hunger and satiety), energy intake (as caloric consumption), and energy expenditure (basal metabolism, thermogenesis, and physical activity) to define long-term body weight.

In humans and animal models, genetic defects in the MC4R pathway, such as POMC deficiency, result in severe forms of early-onset obesity and hyperphagia ([Farooqi 2008](#)). Patients with rare genetic variants in LEPR and patients with BBS, a rare pleiotropic autosomal recessive disorder caused by mutations in as many as 24 different genes, also present with unremitting hunger and severe obesity caused in part by a lack of activation of the MC4R pathway. As a result of hyperphagia, individuals with RGDO have increased calorie intake leading to early-onset, severe obesity, and obesity-related comorbidities such as type 2 diabetes. The Sponsor is developing setmelanotide (also known as RM-493), an MC4R agonist, as a treatment for patients with RGDO. Setmelanotide bypasses upstream signaling defects to directly activate MC4R. Setmelanotide binds with high affinity (inhibitory constant = 2.1 nM) to the human MC4R and is efficient in activating MC4R (50% effective concentration = 0.78 nM).

Thus, setmelanotide has the potential to restore reduced activity in the MC4R pathway in patients with these and other genetic defects, thereby serving as a form of “replacement” therapy to re-establish weight and appetite control in patients with these disorders.

### 1.1.2. Study Objectives

This SAP is designed to outline the methods to be used in the analysis of study data in order to answer the study objective(s). Populations for analysis, data handling rules, statistical methods, and formats for data presentation are provided. The statistical analyses and summary tabulations described in this SAP will provide the basis for the results sections of the clinical study report (CSR) for this trial.

This SAP will also outline any differences in the currently planned analytical objectives relative to those planned in the study protocol.

The study objectives are the following (per protocol):

#### Primary:

- To compare the pharmacokinetics (PK) of the once daily (QD) and once weekly (QW) formulations of setmelanotide

#### Secondary:

- To assess the safety of the QW formulation of setmelanotide with up to 6 months (26 months) of drug administration

[REDACTED]

## 1.2. Study Design

### 1.2.1. Synopsis of Study Design

This study is designed to compare the safety, PK, and [REDACTED] of QD and QW formulations of setmelanotide, as well as to evaluate the safety and [REDACTED] of up to 6 months of QW setmelanotide administration in patients with BBS, biallelic PPL, or heterozygous PPL.

Eligible patients are those who have taken QD setmelanotide in Study RM-493-022 (referred to as the long-term extension [LTE] study) for at least 6 months with acceptable safety and tolerability, and who wish to continue with setmelanotide treatment. Such patients otherwise meet all inclusion and exclusion criteria. Approximately 30 patients will be targeted in 3 age groups as follows: approximately 20 patients  $\geq 18$  years old; approximately 6 patients  $\geq 12$  to  $< 18$  years old; and approximately 4 patients  $\geq 6$  to  $< 12$  years old at the time of study entry.

The study consists of a Screening Period for transition from the LTE study, a Run-in Period of up to 1 week of continuation on the patient's current dose level of QD setmelanotide (2, 2.5, or 3 mg), a 13-week double-blind phase in which the patients will be randomized to either QD or QW setmelanotide, a 13-week non-randomized open-label phase where all patients will receive open-label QW setmelanotide, and a 3-week follow-up period in which all patients will return to their run-in dose level of QD setmelanotide to prepare for re-enrollment into Study RM-493-022 or to resume the QD formulation in some other way.

Once informed consent is provided, patients will enter the Screening Period, during which they will be assessed for eligibility and complete all screening procedures as described in the Schedule of Assessments (SoA) ([Table 1](#)). During the Screening Period, patients will undergo medical evaluation and other study procedures, [REDACTED]. To ensure continuity of treatment, informed consent for this study will be obtained and eligibility of the patient will be confirmed before the patient is withdrawn from the LTE study.

The patient will have a Run-in Period of 1 day to 1 week on QD setmelanotide at the dose they received in the LTE study. The first day of the Run-in Period (Visit 2) should coincide with the patient's last visit in the LTE study to avoid an interruption of treatment. The first dose of QD setmelanotide as part of the RM-493-037 study will occur in clinic on the first day of the Run-in Period. On the first day of the Run-in Period, patients will have serial blood samples taken for measurement of setmelanotide concentrations (QD formulation) and 24-hour PK profiles (including optional timepoint at 12 hours after dosing) will be performed.

On Day 1 (Visit 3) patients will be randomized 1:1 to receive either QD or QW setmelanotide. Patients who received QD setmelanotide at a dose of 2 mg at the time of study entry will be

[figure not shown]
randomized to receive either QD setmelanotide 2 mg or QW setmelanotide at a dose of 20 mg, whereas patients who were on QD setmelanotide at a dose of 2.5 mg will be randomized to receive either QD setmelanotide 2.5 or QW setmelanotide at a dose of 25 mg, and finally patients who were on QD setmelanotide at a dose of 3 mg will be randomized to receive either QD setmelanotide 3 mg or QW setmelanotide at a dose of 30 mg. Study medication will be administered in a double-dummy fashion in order to maintain the double blind. Patients will receive the first QW dose on Day 1 of the randomized treatment period (Visit 3). The randomization will be stratified by age group.

- Patients randomized to QW setmelanotide will receive blinded QW setmelanotide and QD placebo injections until the Week 14 visit (i.e., completion of 13 weeks of blinded dose administration). Starting with Week 14, patients will continue with open-label QW injections of setmelanotide during the 13-week non-randomized phase of the study.
- Patients randomized to QD setmelanotide will receive blinded QD setmelanotide and QW placebo injections until the Week 14 visit (i.e., completion of 13 weeks of blinded dose administration). Starting with Week 14, patients will continue with open-label QW injections of setmelanotide during the 13-week non-randomized phase of the study.

For the 3-week Follow-up Period, all patients will return to their allocated run-in medication of QD setmelanotide to prepare for re-enrollment into Study RM-493-022 or to resume the QD formulation in some other way.

The study design is depicted graphically in [Figure 1](#).

**Figure 1 Study Design Schematic**

### 1.2.2. Randomization Methodology

Patients will be randomized 1:1 on Day 1 (Visit 3) to treatment with either QD or QW setmelanotide, stratified by age group ( $\geq 18$  years old;  $\geq 12$  to  $< 18$  years old;  $\geq 6$  to  $< 12$  years old). The study staff will use an interactive response technology (IRT) system to obtain the randomization number for each patient. To maintain the blind during the 13-week randomized treatment period, all patients will receive placebo injections (from the QD formulation or from the QW formulation) in addition to the setmelanotide injections in a double-dummy fashion. Randomization numbers will not be re-used once assigned. Please refer to the official randomization plan for more details. No randomization or blinding will be done for the 13-week open-label phase or for the 3-week QD follow-up phase.

### 1.2.3. Stopping Rules and Unblinding

Emergency unblinding for adverse events (AEs) may be performed through the IRT system. The IRT system will be programmed with blind-breaking instructions. In case of an emergency, the Investigator has the sole responsibility for determining if unblinding of a patient's intervention assignment is warranted. Patient safety must always be the first consideration in making such a determination. If the Investigator decides that unblinding is warranted, the Investigator should make every effort to contact the Sponsor before unblinding a patient's intervention assignment unless this could delay emergency treatment for the

patient. The date and reason for the unblinding by the Investigator must be recorded. If a patient's intervention assignment is unblinded, the Sponsor must be notified by the Investigator within 24 hours that an unblinding occurrence. The Investigator should not reveal to the Sponsor the patient's treatment allocation unless the Sponsor requests this information for safety purposes.

For any unexpected serious adverse event (SAE) that is treatment-related (e.g., possibly or probably related), the blind will be lifted by the Sponsor only for that specific patient. The blind will be maintained for persons responsible for the ongoing conduct of the study (such as the monitors, investigators, etc.) and those responsible for data analysis and interpretation of results at the conclusion of the study (such as biometrics personnel). Unblinded information will only be accessible to those who need to be involved in the safety reporting to Health Authorities, Ethics Committees, and/or Institutional Review Boards (IRBs). Investigators will receive only blinded information unless unblinded information is judged necessary for safety reasons.

This study may be prematurely terminated, if in the opinion of the Investigator (at a participating site) or Rhythm (for the whole study), there is sufficiently reasonable cause. The terminating party will provide written notification documenting the reason for study termination to either the Investigator or Rhythm. Circumstances that may warrant termination include, but are not limited to:

- Discontinuation of further study intervention development
- Inadequate or no recruitment (evaluated after a reasonable amount of time) of patients by the Investigator
- Total number of patients enrolled earlier than expected

If the study is prematurely terminated or suspended, the Sponsor shall promptly inform the investigators, the IECs/IRBs, the regulatory authorities, and any contract research organization(s) used in the study of the reason for termination or suspension, as specified by the applicable regulatory requirements. The Investigator shall promptly inform the patient and should ensure appropriate patient therapy and/or follow-up.

Every attempt will be made to maintain the blind through the end of the study. Breaking the blind for a patient should be done only in the event of a medical emergency where the identity of study drug is necessary to appropriately treat the patient. As noted above, the Primary Investigator will be provided with access to the IRT system to unblind their patients, but, if possible, the decision to break the blind should first be discussed with the Sponsor. If the blind is broken, the reason, when, and how the blind was broken will be documented.

#### 1.2.4. Study Procedures

The schedule of assessments, as outlined in the study protocol, is provided in **Error! Reference source not found.**

**Table 1 Schedule of Assessments**

Study Period	Screening † (up to 21 days)	Run-In Δ (up to 1 week)	Randomized, Double-Blind Treatment (QD and QW)													Open-Label Non-Randomized QW Administration				Restart QD	Follow - up on QD (EoS)	Early Ter- mi- nation
			V1	V2	V3	V4	V5	V6	V7	V8	V9	V10	V11	V12	V13	V14	V15	V16	V17			
Visit (V) Number	V1	V2	V3	V4	V5	V6	V7	V8	V9	V10	V11	V12	V13	V14	V15	V16	V17	V18	V19	V20	V21	
Study Week	-4	-1	1	2	3	4	5	6	7	8	9	10	11	12	13	14	16	18	22	27	30	
Study Day ± Visit Window	-28 to -8	-7 to -1	1	8 ± 1	15 ± 1	22 ± 1	29 ± 3	36 ± 1	43 ± 1	50 ± 1	57 ± 3	64 ± 1	71 ± 1	78 ± 1	85 ± 1	92 ± 0	106 ± 1	120 ± 3	148 ± 3	183 ± 3	204 ± 3	(n/a)
In Person Visit	X	X	X				X				X					X		X	X	X	X	X
Telehealth Visit 				X	X	X		X	X	X		X	X	X	X		X					
Informed consent/assent	X																					
Inclusion/exclusion review	X		X																			
Medical history & prior medication review	X		X																			
Fitzpatrick scale	X																					
Comprehensive skin exam 	X																			X	X	X
Randomization			X																			
Pregnancy test 	X	X	X†				X†				X†					X†		X†	X†	X†	X†	X†
Study drug: administer 		X	X	X	X	X	X	X	X	X	X	X	X	X	X	X	X	X	X	X	X	X
Study drug dispense 		X	X				X				X					X		X	X	X		
Height 	X		X													X				X		X

Study Period	Screening + (up to 21 days)	Run-In Δ (up to 1 week)	Randomized, Double-Blind Treatment (QD and QW)													Open-Label Non-Randomized QW Administration				Restart QD	Follow-up on QD (EoS)	Early Termination
			V3	V4	V5	V6	V7	V8	V9	V10	V11	V12	V13	V14	V15	V16	V17	V18	V19			
Visit (V) Number	V1	V2	V3	V4	V5	V6	V7	V8	V9	V10	V11	V12	V13	V14	V15	V16	V17	V18	V19	V20	V21	
Study Week	-4	-1	1	2	3	4	5	6	7	8	9	10	11	12	13	14	16	18	22	27	30	
Study Day ± Visit Window	-28 to -8	-7 to -1	1	8 ± 1	15 ± 1	22 ± 1	29 ± 3	36 ± 1	43 ± 1	50 ± 1	57 ± 3	64 ± 1	71 ± 1	78 ± 1	85 ± 1	92 ± 0	106 ± 1	120 ± 3	148 ± 3	183 ± 3	204 ± 3	(n/a)
In Person Visit	X	X	X				X				X				X		X	X	X	X	X	
Telehealth Visit 				X	X	X		X	X	X		X	X	X	X		X					
C-SSRS 	X	X†	X†				X†				X†				X†		X†	X†	X†	X†	X†	
PHQ-9 	X	X†	X†				X†				X†				X†		X†	X†	X†	X†	X†	
Dosing Diary 		X	For each dose administered (QW or QD)																			
PK blood sampling (trough) 			X†				X†				X†				X†		X†	X†	X†			
PK profile 		X													X†							
Injection site inspection 		X	X	X	X	X	X	X	X	X	X	X	X	X	X	X	X	X	X	X	X	
Safety laboratory tests 	X		X								X				X				X	X	X	

Study Period	Screening* (up to 21 days)	Run-In Δ (up to 1 week)	Randomized, Double-Blind Treatment (QD and QW)													Open-Label Non-Randomized QW Administration				Restart QD	Follow- up on QD (EoS)	Early Ter- mi- nation
			V3	V4	V5	V6	V7	V8	V9	V10	V11	V12	V13	V14	V15	V16	V17	V18	V19			
Visit (V) Number	V1	V2	V3	V4	V5	V6	V7	V8	V9	V10	V11	V12	V13	V14	V15	V16	V17	V18	V19	V20	V21	
Study Week	-4	-1	1	2	3	4	5	6	7	8	9	10	11	12	13	14	16	18	22	27	30	
Study Day ± Visit Window	-28 to -8	-7 to -1	1	8 ±1	15 ±1	22 ±1	29 ±3	36 ±1	43 ±1	50 ±1	57 ±3	64 ±1	71 ±1	78 ±1	85 ±1	92 ±0	106 ±1	120 ±3	148 ±3	183 ±3	204 ±3	(n/a)
In Person Visit	X	X	X				X				X					X		X	X	X	X	X
Telehealth Visit 				X	X	X		X	X	X		X	X	X	X		X					
Anti-drug antibodies 			X								X					X				X		X
Vital signs 	X		X	X	X	X	X	X	X	X	X	X	X	X	X	X	X	X	X	X	X	X
ECG (12-lead) 	X		X								X					X				X	X	X
Physical examination 	X		X				X				X					X		X		X	X	X
Activity Sensor Sub-Study (optional)	X	Daily from Screening through the end of the double-blind period																				
Adverse event assessment	X	X	X	X	X	X	X	X	X	X	X	X	X	X	X	X	X	X	X	X	X	X
Concomitant medications review	X	X	X	X	X	X	X	X	X	X	X	X	X	X	X	X	X	X	X	X	X	X

Abbreviations: BP = blood pressure; C-SSRS = Columbia-Suicide Severity Rating Scale; ECG = electrocardiogram; EoS = End of Study; ██████████ HR = heart rate; min = minute; n/a = not applicable; LTE = long-term extension; PHQ-9=Patient Health Questionnaire – 9; PK = pharmacokinetic; QD = once daily; QW = once weekly; V = visit.

\* Due to the rarity of these patients and difficulty associated with travel to the study site, the Screening Period may be extended beyond 3 weeks, if necessary, after discussion with the Sponsor.

Δ The patient will have a Run-in Period of 1 day to 1 week on QD setmelanotide at the dose they were on in the LTE study. The first day of the Run-in Period (V2) should coincide with the patient’s last visit in the LTE study to avoid an interruption of treatment.

† Assessment/sample should be performed/obtained prior to administration of study drug.

 Any telehealth visit may optionally be converted to an in-person visit.

 A comprehensive skin evaluation will be performed by the Investigator. Any concerning lesions identified during the Screening Period will be biopsied and results known to be benign prior to study entry. If the pretreatment biopsy results are of concern, the patient will be excluded from the study.

 A urine pregnancy test may be performed in order to expedite availability of results prior to the first dose at Run-in (V2). All other pregnancy tests will be serum; dosing may continue with results pending.

 For the QD doses of study drug, patients/caretakers will draw up and self-administer/administer the study drug each morning beginning with the first dose of Run-in (V2) and for the duration of the 13-week double-blind period. In addition, once each week the QW dose of study drug will be prepared and administered at the study center or self-administered/administered by the patient/caretaker in between visits. A home healthcare provider can optionally be made available at the patient's home to administer or supervise administration of the QW dose. The patient will receive the first QW dose on Day 1 (V3) at the study center. On the days of in-person clinic visits, the patients/caretakers will self-administer/administer the QD dose of study drug in the clinic in the presence of the clinical staff to assure proper technique. For accountability, patients/caretakers will return all used vials to the clinic when they visit; the study staff will record the number returned; and both study drug administration at the clinic, as well as outpatient study drug administration will be recorded in a study diary.

[REDACTED]

 For patients  $\geq 21$  years of age, height will be measured only during the Screening Period. For patients aged  $< 21$  years, height is to be measured at the time points listed in the SoA. Height (cm) will be measured without shoes, socks or hats using a wall-mounted stadiometer. All measurements will be done in triplicate at each timepoint and recorded to the nearest halfcm. The stadiometer should be calibrated on a daily basis prior to height assessment.

[REDACTED]

[REDACTED]

[REDACTED]

[REDACTED]

 The Baseline/Screening version of the C-SSRS should only be administered to patients who have never completed an initial C-SSRS assessment prior to entering this trial; however, this version is expected to have been completed in the index study for all patients prior to entry into this study. The Screening version of the C-SSRS is to be completed at the Screening visit. At all subsequent visits, the Since Last Version is to be completed. If at any time during the study a patient has suicidal ideation of type 4 or 5, or any suicidal behavior, the patient should be referred to a mental health professional.

 The dosing diary will be completed for all QD and QW dose administration.

[REDACTED]

 Prior to the QW dose of study drug, a blood sample for trough plasma levels of setmelanotide will be drawn within 10 minutes prior to dosing. On the days when 24-hour PK profiles (including optional timepoint at 12 hours after dosing) are done, the predose (trough) PK sample will be drawn within 5 minutes prior to study drug administration. The trough sample to be drawn at Week 14 (V16) will be used as the 168-hour postdose sample for the purpose of the PK profile, therefore no visit window is allowed for Week 14, which must occur exactly 7 days after the last dose of double-blind QW study drug. Patients/caretakers will be reminded that there should be NO study drug administration at home on the day of clinic visits; the drug will be administered in the clinic AFTER the PK sample is obtained. For the PK sample, the actual collection (clock) time will be recorded, as well as the time of the previous day's study drug injection as reported by the patient/caretaker.

 Patients will undergo serial blood samples taken for measurement of steady-state setmelanotide concentrations (both QD and QW) and 24-hour PK profiles (including optional timepoint at 12 hours after dosing) will be performed. On the first day of the Run-in Period, blood samples for the QD PK profile will be drawn within 5 minutes prior to dose administration and at 0.5, 1, and 2 hours ( $\pm 5$  min) postdose and at 3, 4, 6, and 8 hours ( $\pm 10$  min) postdose. At Week 14, blood samples for the PK profiles will be drawn within 5 minutes prior to dose administration and at 0.5, 1, and 2 hours ( $\pm 5$  min) postdose and at 3, 4, 6, and 8 hours ( $\pm 10$  min) postdose and at 24 hours postdose. When possible, additional optional blood draws will be done at 48, 72, 96, 120, and 148 hours. Patients/caretakers will be reminded that there should be NO study drug administration at home on the day of clinic visits and that the predose (trough) blood draw must occur PRIOR to study drug administration. The blood draws for the Week 14 PK sampling must occur exactly 7 days after the prior visit.

 Injection site evaluations and scoring (by the clinical staff) will include identification of areas of erythema, edema, and induration, as well as the presence of localized pain, tenderness, and itching. At in-person study visits, the clinical staff will also record measurements of areas of erythema, edema, and induration if possible. Unscheduled evaluations may also be recorded as warranted by clinical conditions.

 Safety laboratory tests will include: complete blood count with platelet count and standard indices, chemistry panel, coagulation, and urinalysis with microscopic analysis (if positive findings on dipsticks warrant further examination).

 Any patient with a positive ADA at the end of study or early termination will be followed every 3 months after the sample analysis until resolution (ie, no measurable ADA response).

-  All BP and HR measurements are to be obtained in the sitting position following at least 5 minutes of rest. All measurements will be taken in triplicate, approximately 2 minutes apart. When possible, BP should be taken in the non-dominant arm throughout the study, using the same methodology (automated or manual). Body temperature (°C) and respiration rate (breaths/minute) will be obtained in the sitting position following at least 5 minutes of rest.
-  A single 12-lead ECG will be performed with the patient in the supine position following a period of at least 10 minutes of rest.
-  A complete physical examination will be conducted at Screening and at the end of study (Week 30). At other time points, an abbreviated examination, noting any changes from baseline will be performed. In addition, Tanner Staging for assessment of pubertal development will be conducted for those patients who have yet to reach Tanner Stage V. Whenever possible, the same trained health care professional will conduct the examination and Tanner Staging.
-  If at any time during the study an individual patient's PHQ9 score is  $\geq 10$ , the patient should be referred to a Mental Health Professional.

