- ¹⁴ Patients will undergo serial blood samples taken for measurement of steady-state setmelanotide concentrations (both QD and QW) and PK profiles will be performed. On the first day of the Run-in Period, blood samples for the QD PK profile will be drawn within 30 minutes prior to dose administration. Postdose samples will be collected at: 0.5, 1, 2 (±5 mins), 6, 8, 12, and 24 hours (±30 min). At minimum, mandatory postdose samples must be collected at: 6 and 8 hours (±30 min) and at 24 hours (±30 min). At Week 14, blood samples for the PK profiles will be drawn within 30 minutes prior to dose administration. Postdose samples will be collected at: 0.5, 1, 2 (±5 mins), 6, 8, 12, 24, 48, 72, 96, 120, and 168 hours (±30 min). At minimum, mandatory postdose samples must be collected at: 6 and 8 hours (±30 min), 24 hours (±30 min), 48, 72, 96, 120 hours (±30 min), and 168 hours (±30 min) In case of significant challenges with the collection of any PK sample, the investigator should confirm sample prioritization with the sponsor. Patients/caretakers will be reminded that there should be NO study drug administration at home on the day of clinic visits and that the predose (trough) blood draw must occur PRIOR to study drug administration. The blood draws for the Week 14 PK sampling must occur exactly 7 days after the prior visit. The Investigators will adhere to the site-specific blood volume limits for safety laboratory and PK analyses both to ensure minimal distress and reduce the number of venipunctures in pediatric patients. For patients <18 years of age, it may not be possible to collect all labs at every trial visit, though efforts should be made to collect as many PK samples per protocol. Venipuncture reduction is allowed should a patient <18 years of age experience unacceptable discomfort as deemed by the Investigator.

- ¹⁵ Injection site evaluations and scoring (by the clinical staff) will include identification of areas of erythema, edema, and induration, as well as the presence of localized pain, tenderness, and itching. At in-person trial visits, the clinical staff will also record measurements of areas of erythema, edema, and induration if possible. Unscheduled evaluations may also be recorded as warranted by clinical conditions.

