##### **4.4.1. Primary [REDACTED] Analysis**

For the primary [REDACTED] endpoint, the PK profile of the 2 formulations of setmelanotide will be characterized and the steady-state PK parameters ( $C_{max}$ ,  $T_{max}$ ,  $C_{trough}$ ,  $AUC_{0-tau}$ ) will be summarized by dose level and prior treatment regimen (QW or QD) during the double-blind phase of the study using descriptive statistics including n, mean, standard deviation,

geometric mean, minimum, median, maximum, % coefficient of variation (CV), geometric mean CV, and 95% confidence intervals (CIs).

A separate tabulation will be created for the same analysis by subgroup (age category and genetic subgroup).

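### Applied as written, SAP Table 1 footnote 13 would put a 24-hour QD trough at the 168-hour point of the QW profile for QD-arm patients; the protocol instead mandates a real 168-hour sample

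*SAP*

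**What the plan says.** **SAP, Table 1, footnote 13.** "The trough sample to be drawn at Week 14 (V16) will be used as the 168-hour postdose sample". The footnote then gives this use as its reason for fixing the visit day: "therefore no visit window is allowed for Week 14, which must occur exactly 7 days after the last dose of double-blind QW study drug". Neither clause is limited to one arm.

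**SAP, Table 1, footnote 14.** The required Week 14 draws end at 24 h. Later draws, up to 148 h, are optional. No 168-hour postdose draw is listed.

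**SAP 1.2.1.** "patients will be randomized 1:1 to receive either QD or QW setmelanotide". In the control arm, "Patients randomized to QD setmelanotide will receive blinded QD setmelanotide and QW placebo injections until the Week 14 visit". For both arms, "Starting with Week 14, patients will continue with open-label QW injections of setmelanotide during the 13-week non-randomized phase of the study".

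**SAP, Table 1, footnote 4.** QD study drug is a morning injection: "patients/caretakers will draw up and self-administer/administer the study drug each morning beginning with the first dose of Run-in (V2") and through the double-blind period.

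**SAP 4.4.1.** The steady-state parameters Cmax, Tmax, Ctrough and AUC0-tau "will be summarized by dose level and prior treatment regimen (QW or QD) during the double-blind phase of the study".

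**Protocol, Section 2, Table 1.** Footnote 13 keeps the zero window for Week 14 but has no substitution sentence. Footnote 14 lists late Week 14 draws at "24, 48, 72, 96, 120, and 168 hours (±30 min") and includes the 168-hour sample among those that must be collected.

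**The concern.** A predose value can stand in for the concentration at the end of the dosing interval only if the preceding dose was the same drug product and the patient is at steady state. QW-arm patients meet that condition at Week 14. QD-arm patients do not: their last blinded QW injection was placebo, and the drug in their Week 14 predose sample comes from QD dosing. Whether the 168 hours are counted from the Week 13 or the Week 14 injection, that sample contains no QW drug.

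Ctrough and AUC0-tau are both named in the primary endpoint. In the QD arm the comparator formulation would supply the final point of the QW curve. These rows matter because Protocol 5.2 relies on switching patients from daily to weekly drug for the within-patient PK comparison.

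**Working it through.** The plan has no figure to reproduce here: no test, margin or powered sample size is stated. The check has four steps.

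**1. What the Week 14 predose sample is.** Blinded QW injections fall on Days 1, 8, ..., 85 (13 doses). Week 14 is Day 92.
- Since the last blinded QW injection: 92 - 85 = 7 days = 168 h. That injection was active in the QW arm and placebo in the QD arm.
- Since the last QD injection: 92 - 91 = 1 day, about 24 h. That injection was placebo in the QW arm and active in the QD arm.

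The Day 92 dose is the 14th active QW dose in the QW arm and the first in the QD arm.

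**2. How many patients.** With 1:1 allocation of about 30, the QD arm has about 15 (10, 3 and 2 of the planned 20, 6 and 4 by age group).

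**3. Weight of the 168-hour point.** In a linear trapezoid the last concentration carries (168 - previous sample time)/2 hours.

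| Week 14 samples available | Weight | Share of 168 h |
|---|---|---|
| SAP required draws only, to 24 h | (168 - 24)/2 = 72 h | 43% |
| Protocol grid, previous sample at 120 h | (168 - 120)/2 = 24 h | 14% |
| SAP with optional draws to 148 h | (168 - 148)/2 = 10 h | 6% |

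Ctrough does not depend on these weights: if it is read from the 168-hour point, it is replaced outright.

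**4. Size of the AUC change, under assumptions.** The documents give no half-lives. Assumed: one compartment; equal average exposure on the two regimens (QD average set to 1); QD half-life 8, 11 or 16 h; QW release half-life 24, 48, 96 or 168 h; QD absorption from instantaneous to a 1 h half-life. Let ke, ka and kd be ln 2 divided by the QD, absorption and QW half-lives.
- QD concentration t hours after a steady-state dose: Q(t) = 24·ke·ka/(ka - ke) × [exp(-ke·t)/(1 - exp(-24ke)) - exp(-ka·t)/(1 - exp(-24ka))]. The substituted value is Q(24).
- Profile after the first QW dose: C(t) = Q(24 + t) + 168·ke·kd/(kd - ke) × [exp(-ke·t) - exp(-kd·t)].
- AUC change = weight × [Q(24) - C(168)] / AUC on the same grid.

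Example with QD 11 h, QW 96 h, absorption 1 h: Q(24) = 0.470 and C(168) = 0.407, ratio 1.15. On the protocol grid AUC is 118.7, so the change is 24 × 0.063/118.7 = +1.3%. With samples to 24 h only it is 72 × 0.063/116.6 = +3.9%.

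Ratio Q(24)/C(168) with absorption half-life 1 h:

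| QD half-life | QW 24 h | QW 48 h | QW 96 h | QW 168 h |
|---|---|---|---|---|
| 8 h | 5.97 | 1.32 | 0.86 | 0.93 |
| 11 h | 6.74 | 1.69 | 1.15 | 1.27 |
| 16 h | 5.83 | 1.90 | 1.40 | 1.58 |

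With instantaneous absorption the lowest ratio falls to 0.76. Over the whole set:

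| Grid | AUC change |
|---|---|
| Samples to 24 h only | -6% to +18% |
| Protocol grid | -2% to +7% |
| Optional draws to 148 h | -1% to +3% |

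The ends of the first row are 72 × (0.297 - 0.393)/117.3 = -5.9% (QD 8 h, QW 96 h, instantaneous absorption) and 72 × (0.607 - 0.383)/88.5 = +18.2% (QD 16 h, QW 168 h, 1 h absorption). The ranges move with the assumptions: a 2 h absorption half-life gives 0% to +21% on the first grid. If exposure instead followed weekly milligrams (30 against 3 × 7 = 21, a factor of 1.43), dividing the tabulated ratios by 1.43 puts 6 of 12 below 1. These figures isolate the substitution; the interpolation error of a straight line from 24 h to 168 h is not counted.

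**The case against.** The strongest reply is that this is out-of-date schedule text and not an analysis rule. The footnote sits in SAP Section 1, which restates the protocol, and SAP 1.2.4 presents the table as the protocol's schedule. The current protocol has dropped the substitution and collects the real sample. SAP 4.4.1 gives no rule for the 168-hour value, and the PK-parameter part of SAP 1.2.5 is not visible, so an arm-specific rule there cannot be excluded. Much of this stands: bringing the footnotes into line with the protocol removes the defect. Until that is done, the SAP's visible text offers an analyst no 168-hour value other than the trough. The real draw is also easy to miss. It falls on Day 99, with no scheduled visit between Day 92 and Day 106, and the protocol allows fewer venipunctures under age 18 (about 10 of 30 patients).

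A reader might infer three stronger things that the documents do not support:
- *Half the patients will have a corrupted profile.* That follows only if the footnote is applied to the QD arm in place of a sample the protocol mandates.
- *The error pulls the result toward comparability.* The sign changes within plausible assumptions, and no formal comparability decision is planned.
- *The QW estimates as a whole are affected.* The summary is split by prior regimen, so the prior-QW rows are untouched, and for those patients the substitution is sound at steady state.

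**Conclusion.** The point holds in conditional form. As written, the SAP conflicts with the protocol on the 168-hour sample. Followed literally, it would assign a 24-hour QD trough to the end of the QW interval for about 15 of 30 patients, all in the prior-QD rows. That is invalid whatever the sign of the resulting bias. The effect on AUC0-tau depends on which late samples exist: potentially material if draws stop at 24 h, modest on the protocol grid, and small with draws to 148 h. The percentages rest entirely on assumed half-lives, absorption and equal exposure.

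A related limit would remain even with a true 168-hour sample. The QD-arm Week 14 profile follows a first QW dose with QD carry-over, so it is not a steady-state QW profile, although footnote 14 in both documents describes the serial sampling as steady-state. The correction should be made before database lock.

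**What to change.** Amend the SAP as follows:
- Align footnotes 13 and 14 of Table 1 with the protocol's, deleting the substitution sentence and listing the 168-hour postdose draw.
- State that the 168-hour concentration is the observed sample in both arms.
- If that sample is missing, let the Week 14 predose value stand in only for QW-arm patients who took the active Week 13 QW dose. Otherwise leave the 168-hour value missing and flag AUC0-tau.
- Report the QD-arm Week 14 predose value only as a QD trough.
- Label the QD-arm Week 14 profile as a first-QW-dose profile with QD carry-over, and keep it apart from steady-state QW summaries.

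The cost is a few sentences in the SAP and no new samples, because the protocol already requires the draw. The downside is that a few QD-arm profiles may have a flagged or missing AUC0-tau.
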